8.3 Demographics and Other Baseline Characteristics

Demographic and baseline characteristics, including sex, race, ethnicity, age at baseline (both continuous and by categorical summary), weight, height, body mass index (BMI), Kellgren-Lawrence (KL) grade, Widespread Pain Index (WPI), Symptom Severity Question 2 (SSQ2), and investigator-assessed OA laterality will be presented overall and by treatment group. Continuous variables will be summarized with descriptive statistics and categorical variables will be summarized with frequencies and percentages. The summaries will be provided for each analysis set. Subject level listings will also be provided.

8.4 Medical History

A summary of reported medical history will be provided by MedDRA system organ class on the Safety Analysis Set for each treatment group. A subject-level listing will provide further information on each event.

9. EFFICACY ANALYSIS

The statistical hypotheses being tested in this study are:

1. The least squares estimate of improvement from baseline in Pain NRS at Week 12 is greater for subjects who received SM04690 compared to placebo.
2. The least squares estimate of improvement from baseline in WOMAC Function at Week 12 is greater for subjects who received SM04690 compared to placebo.
3. The least squares estimate of improvement from baseline in Pain NRS at Week 24 is greater for subjects who received SM04690 compared to placebo.
4. The least squares estimate of improvement from baseline in WOMAC Function at Week 24 is greater for subjects who received SM04690 compared to placebo.
5. The least squares estimate of improvement from baseline in Patient Global Assessment at Week 12 is greater for subjects who received SM04690 compared to placebo.
6. The least squares estimate of improvement from baseline in Patient Global Assessment at Week 24 is greater for subjects who received SM04690 compared to placebo.

The familywise error rate will be controlled in the strong sense using the closed, fixed sequence testing method (Dmitrienko, Tamhane, & Bretz, 2010). All hypothesis tests will be evaluated in the sequential order as listed above. Although formal hypothesis testing will stop once the first non-significant result is achieved (i.e. $p > 0.05$), all subsequent results and p-values will still be reported for reference; however, no conclusion of statistical significance will be drawn from these results.

9.1 Estimands

The primary estimand for this trial is the difference between a single injection of SM04690 versus placebo in mean baseline-adjusted change in Pain NRS at Week 12, whether or not NSAIDs/acetaminophen are used (i.e. presuming a treatment policy of background NSAID and acetaminophen usage), and analyzed with MMRM, including all collected Pain NRS data in subjects in the FAS.

A summary of all estimands defined for this study is available in [Appendix 3](#).

9.2 Primary Efficacy Analysis

9.2.1 Main Analysis

Change over time in Pain NRS will be characterized using an MMRM model to estimate change from baseline with treatment group, week, treatment \times week interaction and baseline value as covariates. The model will include all timepoints for subjects in the FAS and will be evaluated at Week 12.

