4. STUDY DESIGN

4.1 DESCRIPTION OF THE STUDY DESIGN

This study is a multicenter, randomized, double-blind, placebo-controlled, parallel group study of a single dose of SM04690 injected into the target knee joint of moderately to severely symptomatic OA subjects at Day 1.

Approximately 726 subjects will be enrolled and randomized at a ratio of 1:1 (0.07 mg active per 2 mL injection: 2 mL Placebo). Subjects will participate in a 7- to 11-day screening period followed by a single injection and a 28-week evaluation period. Clinic visits will be scheduled at the Screening Visit, Day 1, and Weeks 4, 12, 24, and 28 (EOS)/ET. Phone visits will be scheduled at Weeks 8, 16, and 20. Specific timing of protocol procedures is described in the Schedule of Events Table ([Section 7.3.7](#)). Specific timing of electronic diary and questionnaire completion is described in the Schedule of Electronic Diary and Questionnaire Completion Table ([Section 7.3.8](#)).

This study will be conducted at approximately 100 investigational centers.

A Widespread Pain Index and Symptom Severity (WPI&SS) assessment will be administered at the Screening Visit and Day 1.

Subjects will be required to complete an electronic diary for the following ([Section 7.3.8](#)):

- Daily pain NRS from the Screening Visit through Week 28 (EOS)
- WOMAC at baseline and Weeks 4, 12, 24, and 28 (EOS)
- Patient Global Assessment at baseline and Weeks 4, 12, 24, and 28 (EOS)

In addition, general medical evaluations including physical examination, knee examination, and recording of vital signs will be performed at the Screening Visit, Day 1, and Weeks 4, 12, 24, and 28 (EOS)/ET. Height will be measured at the Screening Visit and weight will be measured at the Screening Visit and Weeks 28 (EOS)/ET. Clinical laboratory evaluations will be performed at the Screening Visit and Weeks 4, 12, 24, and 28 (EOS)/ET. Investigator assessment of NSAID/acetaminophen usage will be performed at all in-person and phone visits starting at Day 1.

Recording of signs and symptoms of study medication intolerance and AE reporting will start following the injection of the study medication and continue at all subsequent in-person and phone visits until the subject completes Week 28 (EOS)/ET. All AEs, whether volunteered, elicited, or noted during examination, will be recorded throughout the study.

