10.4.2 ANALYSIS OF THE PRIMARY ENDPOINT

Change over time in weekly average of daily pain NRS will be characterized using a mixed-effects model for repeated measures (MMRM) in order to estimate change from baseline with treatment group, week, treatment \times week interaction and baseline value as covariates. The model will be evaluated at Week 12. Unadjusted 95% confidence intervals and *P* values will be reported. The potential confounding effect of change in NSAID/acetaminophen usage on the treatment effect will be considered for sensitivity analysis.

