5. SAMPLE SIZE DETERMINATION

A sample size of approximately 725 subjects was initially selected for this study to yield 325 evaluable subjects per treatment group assuming 10% dropout.

One thousand Monte Carlo simulations generated baseline and follow-up data from a bivariate normal distribution for each treatment group and estimated the least squares difference between treatment and placebo in an outcome's change using a baseline-adjusted analysis of covariance (ANCOVA). The proportion of statistically significant results at $\alpha = 0.05$ was estimated as the approximate power for a sample size of 325 subjects per group.

The following assumptions were made based upon observed data in the Phase 2 dose-ranging studies (SM04690-OA-02 and SM04690-OA-04):

- For Pain NRS, assuming a baseline mean (standard deviation [SD]) of 6.0 (1.5), follow-up mean (SD) of 3.0 (3.0) for SM04690 and 3.8 (3.0) for placebo (presumed treatment difference -0.8), and a baseline to follow-up correlation of 0.25, power is estimated to be 93.5%.
- For WOMAC Function, assuming a baseline mean (SD) of 60 (14), follow-up mean (SD) of 30 (29) for SM04690 and 37.5 (29) for placebo (presumed treatment difference -7.5), and a baseline to follow-up correlation of 0.25, power is estimated to be 92.0%.
- For Patient Global Assessment, assuming a baseline mean (SD) of 55 (20), follow-up mean (SD) of 35 (27) for SM04690 and 42.5 (27) for placebo (presumed treatment

difference -7.5), and a baseline to follow-up correlation of 0.25, power is estimated to be 95.3%.

Based upon a blinded evaluation of aggregate data, sample size assumptions were reassessed, and additional Monte Carlo simulations generated. A sample size of approximately 500 subjects was re-estimated for this study to yield 225 evaluable subjects per treatment group assuming 10% dropout.

- For Pain NRS, assuming a baseline mean (standard deviation [SD]) of 6.0 (1.2), follow-up mean (SD) of 3.0 (2.4) for SM04690 and 3.8 (2.4) for placebo (presumed treatment difference -0.8), and a baseline to follow-up correlation of 0.25, power is estimated to be 94.3%.
- For WOMAC Function, assuming a baseline mean (SD) of 60 (12), follow-up mean (SD) of 30 (25) for SM04690 and 37.5 (25) for placebo (presumed treatment difference -7.5), and a baseline to follow-up correlation of 0.25, power is estimated to be 89.8%.

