7.1.2 Mixed-Effects Model for Repeated Measures

A mixed-effects model for repeated measures (MMRM) will be used to evaluate Pain NRS, WOMAC, and Patient Global Assessment outcome measures. The null hypothesis is that the mean difference in the endpoints between the two treatment groups is zero, versus the alternative hypothesis that this difference is not zero. The hypotheses can be expressed as follows:

$$H_0: (\beta_1 - \beta_0)_t = 0$$

$$H_A: (\beta_1 - \beta_0)_t \neq 0,$$

where β_0 refers to the least squares mean change from baseline in the placebo group and β_1 refers to the least squares mean change from baseline in the active treatment group, evaluated at timepoint t .

For Pain NRS, the model will be estimated assuming a Toeplitz variance-covariance matrix. The Toeplitz structure is a more generalized form of autoregressive-1 (AR1) structure, allowing the data to inform how the correlation between within-subject observations decreases over time instead of implicitly defining a uniform decay structure (Kincaid, 2005).

For WOMAC and Patient Global Assessment, the model will be estimated assuming an unstructured variance-covariance matrix, allowing the data to fully inform the correlation between within-subject observations (Kincaid, 2005).

MMRM presumes that missing data are not caused by something observable within the conduct of the trial (i.e. missing-at-random [MAR]). It is plausible to presume a MAR mechanism as there have been no observed tolerability issues to the administration of study injection during the prior development trials. Additionally, the study injection cannot be removed after it has been administered, eliminating study drug discontinuation as a source of treatment estimate confounding.

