7.3 Efficacy Assessments

7.3.1 Pain NRS

The Pain NRS is an 11-point scale [0-10] for subject self-reporting of average knee pain in the previous 24 hours, where 0 represents no pain and 10 represents extreme pain. Subjects were prompted to report average pain in both knees daily on their electronic device (between 5:00 pm and 11:59 pm) during the screening period and on the target knee only starting from Day 1 through the end of the study. An average weekly score (referred to as Pain NRS) was calculated for each subject if they had provided a response for at least 4 out of 7 days in a given week. Weeks are defined as Day -7 through Day -1 (day before treatment) for baseline, Day 1 (day of treatment) through Day 7 for Week 1, Day 8 through Day 14 for Week 2, and so on as detailed in [Appendix 1](#). The day on which subjects completed their scheduled study visits (e.g. Week 4 Visit, Week 12 Visit, etc.) does not impact the above definition of weeks.

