9.3 Secondary Efficacy Analysis

9.3.1 Main Analysis

Change over time in secondary endpoints will be characterized using MMRM to estimate change from baseline with treatment group, week, treatment \times week interaction and baseline value as covariates. The model will include all timepoints for subjects in the FAS and will be evaluated for Pain NRS at Week 24 and WOMAC Function and Patient Global Assessment at Weeks 12 and 24.

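### Every MMRM fits one baseline slope across all weeks; adding a baseline × week term would be a small, nearly free gain in precision and consistency

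*SAP*

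**What the plan says.** The fixed effects are the same wherever an MMRM is specified: treatment group, week, treatment × week and baseline value.

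- Protocol 10.4.2 (primary) ends its list of terms this way: "week interaction and baseline value as covariates. The model will be evaluated at Week 12". Protocol 10.4.3 and 10.4.5 use the same list.
- SAP 9.2.1 (primary) keeps that list and brings every timepoint into the fit; its wording is "week interaction and baseline value as covariates. The model will include all timepoints for subjects in the FAS". SAP 9.3.1 does likewise in the secondary models, which cover Week 24 for Pain NRS and both Week 12 and Week 24 for the other two scales. SAP 9.4 and Appendix 3 repeat the list.
- Covariance, SAP 7.1.2: "For Pain NRS, the model will be estimated assuming a Toeplitz variance-covariance matrix". The other two scales are treated differently there: "For WOMAC and Patient Global Assessment, the model will be estimated assuming an unstructured variance-covariance matrix".
- Timepoints: Pain NRS is averaged by week, "Day 1 (day of treatment) through Day 7 for Week 1, Day 8 through Day 14 for Week 2, and so on" (SAP 7.3.1), taken here as Weeks 1 to 28. Protocol 4.1 schedules "WOMAC at baseline and Weeks 4, 12, 24, and 28 (EOS"), and Patient Global at the same visits.

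The power simulation used a different model. SAP 5 says that it "estimated the least squares difference between treatment and placebo in an outcome's change using a baseline-adjusted analysis of covariance (ANCOVA"), at a single follow-up time. The Appendix 3 sensitivity analyses are also baseline-adjusted ANCOVAs at the tested week, and SAP 7.1.6 imputes each timepoint separately from baseline.

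**The concern.** With baseline as a main effect only, the model estimates one slope and applies it at every week. The slope of follow-up pain on baseline need not be constant. Week 1 starts straight after the baseline week, so a stronger link there than at Week 12 or Week 24 is plausible. Where the common slope differs from a tested week's own slope, part of any chance baseline difference between arms stays in the tested contrast, and some variance that baseline could explain goes unexplained.

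All six hypotheses in the fixed sequence rest on these models. WOMAC Function at Week 12 is second, so a test lost there stops formal testing of the remaining four. There is also a point of interpretation. The main MMRM uses a common slope and Sensitivity 1 uses the tested week's own slope. A gap between the two results would therefore mix a change in baseline adjustment with a change in missing-data handling.

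**Working it through.** **Inputs from SAP 5 (re-estimated design).** 225 evaluable per arm. Pain NRS: baseline SD 1.2, follow-up SD 2.4, difference −0.8. WOMAC Function: baseline SD 12, follow-up SD 25, difference −7.5. Baseline to follow-up correlation 0.25, with no week attached; it is placed at Week 12 here. Two-sided α = 0.05.

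**Reproducing the stated power.** Residual SD = SD × √(1 − r²); SE = residual SD × √(2/n); power = Φ(difference/SE − 1.96).

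- Pain NRS: 2.4 × √0.9375 = 2.324; SE = 2.324 × √(2/225) = 0.219; Φ(3.65 − 1.96) = 95.5% (SAP: 94.3%).
- WOMAC Function: 25 × √0.9375 = 24.21; SE = 2.282; Φ(3.29 − 1.96) = 90.8% (SAP: 89.8%).

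Both are within 2 points of the simulated figures. They describe a model with the tested week's own slope.

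**Own-week slope.** b_t = r_t × SD_t / SD_baseline. Pain NRS at Week 12: 0.25 × 2.4/1.2 = 0.50. WOMAC Function at Week 12: 0.25 × 25/12 = 0.52.

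**Common slope.** With complete data the fitted slope tends to b_c = (1′V⁻¹b)/(1′V⁻¹1), where b holds the weekly slopes and V is the within-subject covariance. Then:

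- residual in the contrast at week t = (b_t − b_c) × baseline imbalance
- variance inflation = (b_t − b_c)² × SD_baseline² / residual variance

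A 1-SD imbalance is 1.2 × √(2/225) = 0.113 NRS points, or 12 × √(2/225) = 1.13 WOMAC points.

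**Where the weight falls, Pain NRS.** The inverse of a symmetric Toeplitz matrix is unchanged when the order of weeks is reversed. Weeks 1 and 28 therefore carry equal weight, and Weeks 1–14 and 15–28 carry 0.50 each. In the AR(1) case the end weight is 1/(28 − 26ρ): 1/7.2 = 0.14 at ρ = 0.80 and 1/3.3 = 0.30 at ρ = 0.95. Week 1 is influential, but Week 28 is equally so.

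**Results, Pain NRS.** Assumed, not in the documents: correlation with baseline 0.4–0.8 at Week 1 and 0.10–0.25 at Week 28; Week 1 SD 1.6–2.4; 18 scenarios.

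| | Week 12 | Week 24 |
|---|---|---|
| b_t − b_c | −0.36 to +0.10 (positive in 4 of 18) | −0.49 to −0.02 |
| Largest residual per 1-SD imbalance | 0.36 × 0.113 = 0.04 | 0.49 × 0.113 = 0.055 |
| Variance inflation | 0% to 3.5% | up to 6.0% |
| Power lost | at most 95.5% − 94.8% = 0.7 points | 0 to 1.2 points |

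Check on the Week 12 maximum: 0.36² × 1.2² / 2.324² = 0.1296 × 1.44 / 5.40 = 3.5%.

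**Results, WOMAC Function.** Assumed: Week 4 correlation 0.35, 0.50 or 0.70; Week 28 correlation 0.15 or 0.25; Week 4 SD 18 or 25. Weeks 4 and 12 together carry 57% to 97% of the slope weight.

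| Week 4 correlation | Largest inflation, Week 12 | Largest inflation, Week 24 | Lowest power, Week 12 | Lowest power, Week 24 |
|---|---|---|---|---|
| 0.35–0.50 | 2.0% | 3.5% | 90.2% | 88.8% |
| 0.70 | 17% | 22% | 85.9% | 83.2% |

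The own-slope power is 90.8% at Week 12. In the scenarios that give the Week 24 minima it is 89.8%. The largest residuals per 1-SD imbalance, both at correlation 0.70, are 0.95 points (Week 12) and 1.10 points (Week 24), against an effect of 7.5. Inflation reaches roughly 5% or more only once the Week 4 correlation is about 0.6 or higher.

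**Limits.** The formulas assume complete data; dropout would remove late weeks and move some weight to earlier ones. Patient Global was not computed; it shares WOMAC's schedule and covariance structure.

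**The case against.** The strongest reply is that nothing is invalid here. Protocol and SAP agree on the specification, and allocation is randomised 1:1 in permuted blocks, so the residual averages zero over repeated trials. That stands. A reader might infer a biased treatment effect or an inflated type I error; the documents support neither.

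A reader might also infer that the Week 12 Pain NRS slope must be pulled toward the early weeks. It need not be. Week 12 lies near the middle of the series, the Toeplitz weights are symmetric, and later weeks can offset early ones. A falling correlation does not by itself mean a falling slope either: r = 0.50 with SD 1.2 at Week 1 gives 0.50 × 1.2/1.2 = 0.50, the same slope as r = 0.25 with SD 2.4 at Week 12. The documents give one correlation and no week-specific SDs, so unequal slopes remain an assumption.

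Finally, the Appendix 3 ANCOVAs already fit the tested week's slope and would show a material discrepancy. That is a real safeguard, but only as sensitivity analysis; the confirmatory tests still use the common slope. The objection reduces the point to a refinement and does not remove it.

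**Conclusion.** The omission is certain: no MMRM in either document includes baseline × week. Its consequence depends on slopes that differ by week, which is plausible but unreported. If the slopes are equal, there is no residual and no loss.

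For the primary endpoint the effect is small on every pattern tried, and its direction is not fixed. At Week 24 the Pain NRS gap ran toward the earlier weeks in every scenario, still with modest cost. WOMAC Function is more exposed because it has only four visits, but a sizeable loss needs a high Week 4 correlation that nothing in the documents establishes. This is an optional improvement in efficiency and consistency, and not a validity error.

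**What to change.** Before unblinding, state the covariates as treatment group, week, treatment × week, baseline value and baseline × week in SAP 9.2.1, 9.3.1, 9.4 and the MMRM rows of Appendix 3, and in Protocol 10.4.2, 10.4.3 and 10.4.5 (or record the change in SAP 13).

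The cost is 28 − 1 = 27 degrees of freedom for Pain NRS and 4 − 1 = 3 for WOMAC and Patient Global, negligible with about 450 evaluable subjects. If the slopes prove equal, almost nothing is lost. The main MMRM and Sensitivity 1 would then adjust for baseline in the same way, so a gap between them would be easier to attribute to missing-data handling. The Pain NRS standard errors would still differ somewhat from ANCOVA, because the Toeplitz matrix pools one variance over all weeks.

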4.2 Method of Treatment Assignment and Randomization

Subjects were randomized 1:1 (0.07 mg active per 2 mL injection:2 mL placebo) to each treatment group using Medidata Rave Randomization and Trial Supply Management (RTSM) with a permuted block design stratified by study site. 250 blocks of size 6 were generated for a total of 1500 possible subject slots.

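### All six models in the test hierarchy adjust only for the outcome's own baseline (about 6% of variance on the plan's own assumption); KL grade and baseline NSAID/acetaminophen use are collected and could add modest precision

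*SAP*

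**What the plan says.** - **Main models.** SAP 9.2.1 (primary) and 9.3.1 (secondary) specify an MMRM with treatment group, week and the treatment × "week interaction and baseline value as covariates". Protocol 10.4.2 and 10.4.3 give the same list. SAP Section 9 tests six hypotheses in fixed order: Pain NRS, WOMAC Function and Patient Global, each at Weeks 12 and 24. All six use this model. The ANCOVA in SAP 7.1.3 also adjusts only for the outcome's baseline.
- **Planning assumption.** SAP Section 5 states for the re-estimated WOMAC Function calculation "a baseline to follow-up correlation of 0.25, power is estimated to be 89.8" per cent. Pain NRS uses the same correlation, with stated power 94.3%. On size: "A sample size of approximately 500 subjects was re-estimated for this study to yield 225 evaluable subjects per treatment group assuming 10% dropout".
- **KL grade.** Inclusion criterion 4 (Protocol 5.1) requires grade 2 or 3 from independent central readers, so the value should be present for nearly everyone. SAP 8.3 lists it as a descriptor only: "Kellgren-Lawrence (KL) grade, Widespread Pain Index (WPI), Symptom Severity Question 2 (SSQ2").
- **Baseline NSAID/acetaminophen use.** Protocol 7.1.1 has the name, usual daily dose and usual days per week over the previous four weeks recorded on Day 1 before injection, on a dedicated form. SAP 12.3 defines a Total NSAID Score for Day -28 to Day -1 and sets it to 0 for non-users.
- **The one model with another covariate.** Sensitivity 2 in SAP Appendix 3 adds the change in Total NSAID Score, a post-randomisation quantity.

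**The concern.** A covariate measured before randomisation that predicts the outcome narrows the standard error of the treatment comparison. It does not alter the treatment-policy estimand in SAP 9.1, and it does not inflate the type I error if it is fixed in advance. Here the only covariate is one that the plan expects to explain little. Two other pre-injection variables are in hand and play no part in the tested models.

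WOMAC Function at Week 12 has the most to gain. It is second in the sequence, so missing it ends formal testing of the four hypotheses behind it. Its stated power is 89.8% after the reduction from 325 to 225 evaluable subjects per group. The stake is a little precision on tests that are otherwise soundly set up.

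**Working it through.** **Inputs (SAP Section 5 unless stated)**
- Two-sided test at 0.05; SAP 7.1.2 sets the null "versus the alternative hypothesis that this difference is not zero".
- n = 225 evaluable per group, 1:1 (SAP 4.2).
- Pain NRS: difference 0.8, follow-up SD 2.4. WOMAC Function: difference 7.5, follow-up SD 25.
- Baseline to follow-up correlation 0.25.
- Joint partial correlation r of KL grade and baseline use with the outcome, given its baseline: **not in the documents; assumed 0.10, 0.20 and 0.25.**

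**Step 1. What the planned covariate explains.** 0.25² = 0.0625, or 6.25%.

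**Step 2. Reproduce the plan's power.** SE = SD × √(1 − 0.0625) × √(2/225); noncentrality = difference / SE; power = Φ(noncentrality − 1.96).
- Pain NRS: SE = 2.4 × 0.9682 × 0.0943 = 0.219; 0.8/0.219 = 3.651; power 95.5% (stated 94.3%).
- WOMAC Function: SE = 25 × 0.9682 × 0.0943 = 2.282; 7.5/2.282 = 3.286; power 90.8% (stated 89.8%).

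A 5,000-run ANCOVA simulation gave 95.3% and 91.0%. The plan used 1,000 runs, so its 95% Monte Carlo margins are 1.96 × √(0.943 × 0.057/1000) = 1.4 points and 1.96 × √(0.898 × 0.102/1000) = 1.9 points. The stated figures are reproduced within those margins. The sample size also reproduces: 225/0.9 = 250 per group, 500 in all.

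**Step 3. Add the two covariates.** Residual variance is multiplied by (1 − r²), so noncentrality is divided by √(1 − r²). Equivalent extra subjects = 450/(1 − r²) − 450.

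| Assumed r | Variance cut | Extra subjects | Pain NRS power | WOMAC Function power |
|---|---|---|---|---|
| 0 (as planned) | 0 | 0 | 95.5% | 90.8% |
| 0.10 | 1% | about 5 | 95.6% | 91.0% |
| 0.20 | 4% | about 19 | 96.1% | 91.8% |
| 0.25 | 6.25% | 30 | 96.5% | 92.4% |

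From the rounded figures, the gain is 0.1 to 1.0 points for Pain NRS and 0.2 to 1.6 for WOMAC Function. Section 5 gives no re-estimated assumptions for Patient Global, so no figure is offered there.

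**Step 4. A smaller true effect.** If the Pain NRS difference were 0.5 (assumption), a 5% cut in residual variance would raise power from 62.6% to 64.9%.

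**Step 5. Worst case.** With useless covariates, residual degrees of freedom fall from 447 to 445. The SE factor is √(447/445) = 1.002.

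**Step 6. How much KL grade alone could give.** With a 50/50 split of grades 2 and 3 (assumption), explaining a share R² of residual variance needs a gap between grades of √(R²/0.25) × 2.4 × 0.9682 NRS points. That is 0.46 for 1% and 0.93 for 4%; the latter exceeds the planned treatment effect of 0.8.

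**The case against.** The strongest case for leaving the plan alone is that nothing in it is wrong. A baseline-adjusted MMRM is unbiased under randomisation, and the covariate list matches the protocol. The whole gain in Step 3 lies inside the Monte Carlo margin of the plan's own power figures. KL grade has only two levels, from a radiograph up to 24 weeks old. The NSAID score rests on four-week recall, banded frequencies and some dose equivalences set by the sponsor's medical director. All of this stands. It limits the size of the point but does not remove it, because the worst case costs almost nothing.

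A reader might infer four stronger things that the documents do not support:
- **That every efficacy model uses the outcome's baseline alone.** Sensitivity 2 does not. Its extra term arises after randomisation and may be affected by treatment, so it does not supply the precision at issue.
- **That the plan itself treats baseline analgesic use as a confounder.** Protocol 10.4.2 and SAP 9.2.2 speak of change in usage. Baseline use cannot bias a randomised comparison, and exclusion criterion 29 requires users to have been on a stable regimen for four weeks.
- **That adjustment would sharpen the tests.** No document gives the prognostic strength of either variable. The top of the assumed range has the pair adding as much as the plan credits to the outcome's own baseline.
- **That the change is free.** It departs from the protocol's covariate list and reaches beyond the main-model sections.

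**Conclusion.** The point holds as a modest efficiency gain, not as a flaw in validity. All six tested models rely on one covariate that the plan expects to explain 6.25% of variance, while two collected pre-injection variables go unused. Over the assumed range the benefit is worth about 5 to 30 subjects on 450. The result rests on the plan's own effects, SDs and correlation, on a normal approximation for a single time point, and above all on an assumed prognostic strength that the documents do not let anyone check. It is an optional improvement, and confidence that the gain would be noticeable is low.

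**What to change.** Before unblinding:
1. In SAP 9.2.1, 9.3.1 and 7.1.3, add KL grade (2 or 3) and baseline NSAID/acetaminophen use as fixed covariates.
2. Take baseline use from the dose and days per week on the Day 1 form. SAP 12.1 sets a start date known only to the year or month of injection to the injection date itself, which can erase that drug's use from the Day -28 to Day -1 window. With duration set to the full 28 days, the SAP 12.3 formula reduces to equivalent dose × usual usage and needs no start date.
3. Put the same terms in the imputation model (SAP 7.1.6) and in the estimand rows of Appendix 3. State how Sensitivity 2 will handle baseline use alongside its change, and which baseline definition that change is measured from.
4. Declare the change in SAP Section 13 and keep the protocol's baseline-only model as a supportive analysis.

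The cost is SAP wording, two model terms from data already collected, and a declared departure from the protocol's covariate list. If treatment codes are already known, the adjusted model should be only a labelled supportive analysis.
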